2. PARTICIPANTS

2.1. [DETERMINATION] **Participants.** Describe the general characteristics of the subject populations or groups, including age range, gender, health status, and any other relevant characteristics.

Adults with MS who report at least moderate fatigue.

2.2. [DETERMINATION] **Inclusion and exclusion criteria.**

2.2.a. Inclusion criteria. Describe the specific criteria that will be used to decide who will be included in the research from among interested or potential subjects. Define any technical terms in lay language.

- (1) MS diagnosis of any subtype per chart review
- (2) Score 4 or higher on the Fatigue Severity Scale
- (3) Are able to comply with study procedures and complete measures independently assessed via self-report
- (4) All genders
- (5) 18 years of age or older
- (6) Able to read and speak English
- (7) Has experienced fatigue for 3 or more months
- (8) Are willing to maintain current fatigue treatment regimen for duration of study (although individuals who want to make a change to their fatigue treatment regimen will be considered eligible 3 months after making that change)

2.2.b. Exclusion criteria. Describe the specific criteria that will be used to decide which of the subjects who meet the inclusion criteria listed above will be excluded from the research. Define any technical terms in lay language.

- (1) Score greater than 7 on the Patient Determined Disease Steps Scale
- (2) Has significant cognitive impairment as indicated by 1 or more errors on the 6-item Cognitive Screener
- (3) Change in disease modifying medications in the prior three months assessed via self-report (although participants will be considered eligible after the 3-month window)
- (4) History of MS relapse within the last 30 days prior to screening assessed via self-report (although participants will be considered eligible after the 30-day window)
- (5) Current suicidal ideation with intent or plan as indicated by a score of 1 or higher on the Patient Health Questionnaire-9 suicide item and further assessment with the Columbia-Suicide Severity Rating Scale (although individuals with suicidal ideation but no intent or plan will be considered eligible)
- (6) Currently engaged in psychotherapy for fatigue assessed via self-report
- (7) Current pregnancy (although participants will be considered eligible when they are no longer pregnant)
- (8) Inability to read or speak English

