5. Does the person score 4 or higher on the Fatigue Severity Scale? _____
6. Has the person experienced fatigue for 3 or more months? _____
7. Is the person willing to maintain current fatigue treatment regimen for duration of study (although individuals who want to make a change to their fatigue treatment regimen will be considered eligible 3 months after making that change)? _____

Must be no to qualify

8. Does the person score 7 or higher on the Patient Determined Disease Steps Scale? _____
9. Does the person have significant cognitive impairment as indicated by 1 or more errors on the 6-item Cognitive Screener? _____
10. Did the person change disease modifying medications in the prior three months (although participants will be considered eligible after the 3-month window)? _____
11. Did the person have an MS relapse within the last 30 days prior to screening (although participants will be considered eligible after the 30-day window)? _____
12. Does the person have current suicidal ideation with intent or plan as indicated by a score of 1 or higher on the Patient Health Questionnaire-9 suicide item and further assessment with the Columbia-Suicide Severity Rating Scale (although individuals with suicidal ideation but no intent or plan will be considered eligible)? _____
13. Is the person currently engaged in psychotherapy for fatigue? _____
14. Is the person pregnant (although participants will be considered eligible when they are no longer pregnant)? _____
15. Is the person participating in another research study that could impact fatigue (although individuals can be screened for eligibility again once they have completed the other research study)? _____

The PHQ-9 suicide item and Columbia-Suicide Severity Rating Scale may reveal suicide ideation. More detail is in Section 10.10.

4.2. Recruitment materials.

4.2.a. What materials (if any) will be used to recruit and screen subjects?

Examples: talking points for phone or in-person conversations; video or audio presentations; websites; social media messages; written materials such as letters, flyers for posting, brochures, or printed advertisements; questionnaires filled out by potential subjects.

Info on MS Clinic provider recruitment reference sheet, recruitment script, screening form, and email. We will not post flyers in the clinic given the robust Research Center Pool.

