All study activities will be completed remotely via Zoom or over the phone over the approximately 2 months. Participants will complete a baseline self-report assessment via REDCap (or by telephone, if preferred) that will take approximately 30-45 minutes to complete. At this time, they will also complete a medication collection form with research staff by phone and will be randomly assigned to one of three 4-session telehealth CBT intervention components: (1) relaxation training, (2) behavioral activation, or (3) cognitive therapy. Prior to starting their assigned intervention component, participants will complete a survey consisting of four to eight questions about their fatigue twice per day (morning and evening) for seven days via REDCap (or by telephone, if preferred). They will then complete the 4-session intervention to which they are randomly assigned in approximately 4 weeks. After completing the first intervention session, participants will complete a treatment expectancy measure via REDCap (or by telephone, if preferred). After completing the intervention, participants will complete the post-intervention self-report assessment via REDCap (or by telephone, if preferred) within one month of the last intervention session. During this time, they will also complete a medication collection form with research staff by phone and a survey consisting of four to eight questions about their fatigue twice per day (morning and evening) for seven days via REDCap (or by telephone, if preferred). Qualitative interview data will supplement the quantitative data collected in the post-intervention assessment. Study staff will conduct and audio record semi-structured interviews within one month of completing the last intervention session to query participants about feasibility, acceptability, appropriateness, and perceived efficacy of the intervention component they completed to inform potential component refinement.

5.2. **[DETERMINATION] Recordings.** Does the research involve creating audio or video recordings?

No → Go to [question 5.3](#).

Document Date & Version	APPLICATION IRB Protocol	Researcher Date & Version
01.26.2023 Version 4.3		05/02/2024 Version 1.5 Page 21 of 61

Yes → Verify that you have described what will be recorded in the answer to [question 5.1.](#), and answer question the question below.

5.2.a. Before recording, will consent for being recorded be obtained from subjects and any other individuals who may be recorded?

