After providing informed consent, research staff will ask the participant to provide demographic data (e.g., age, sex, gender orientation, ethnicity/race, marital status, education level, income, household size, disability compensation status, lawsuit status, employment status) for descriptive purposes. We will also ask participants to complete validated self-report questionnaires (demographics, MS disease-related variables, quality of life, and biopsychosocial symptom variables [e.g., fatigue]). We will also ask participants to complete a survey consisting of four-eight questions about their fatigue twice per day (morning and evening) for seven days (each survey should take less than 5 minutes).

Personal Contact Information

Research staff will collect the following information from participants: (1) contact information; (2) preferred telephone number to reach an individual if they have more than one line; (3) permission to leave message on mobile/landline phones; (4) permission to send a text message and, if yes, cell phone carrier; (5) best times/days to reach participant; (6) email address; (7) preferred communication method; and (8) names and contact information of people staff are allowed to contact if participant is lost to follow-up or otherwise cannot be contacted (i.e., collateral contacts).

We will gather data either from the participant directly or in the form of online self-report assessments via a password-protected database on the department's secure server.

Treatment Expectancy Assessment

Participants will complete the Credibility/Expectancy Scale after the first intervention session.

Medication collection form (pre- and post-treatment)

Participants will be asked questions about the medications they are taking (e.g., name, indication, dosage, dose units)

Post-Intervention Assessment

Participants will be asked questions about quality of life and biopsychosocial symptom variables (e.g., fatigue). We will also ask participants to complete a survey consisting of four-eight questions about their fatigue twice per day (morning and evening) for seven days (each survey should take less than 5 minutes).

Post-Intervention Qualitative Interview

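### The entry rules ask about past changes in disease-modifying medication but not about a change already planned, so such a change can fall between the pre and post measures

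*Protocol*

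**What the plan says.** Two entry rules bear on stability of treatment, and they face in different directions.

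- **Looking back.** Section 2.2.b, exclusion (3), is "Change in disease modifying medications in the prior three months assessed via self-report". The person becomes eligible once the three-month window has passed. Section 4.1, screening question 10, repeats it in the past tense: "Did the person change disease modifying medications in the prior three months".
- **Looking forward.** Section 2.2.a, inclusion (8), admits people who "Are willing to maintain current fatigue treatment regimen for duration of study". Screening question 7 is worded the same way: "Is the person willing to maintain current fatigue treatment regimen for duration of study". Someone who wants to change that regimen is deferred and may enter three months after the change.

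Disease-modifying medication is a separate item from the fatigue regimen in both lists. No other criterion in section 2.2 and no other question in section 4.1 asks about a medication change still to come.

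On timing, section 5.1 says "All study activities will be completed remotely via Zoom or over the phone over the approximately 2 months". A week of twice-daily fatigue surveys comes before treatment. Then, "They will then complete the 4-session intervention to which they are randomly assigned in approximately 4 weeks". The post-intervention assessment follows "within one month of the last intervention session".

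Medications are recorded by phone before and after treatment. Section 5.4 describes the form this way: "Participants will be asked questions about the medications they are taking (e.g., name, indication, dosage, dose units".

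**The concern.** For the fatigue regimen the protocol guards both directions: no change during the study, and a wait after one. For disease-modifying medication it guards only the past. Followed as written, the rules defer someone who changed medication last month and admit someone due to change next week, although the second change is the one that lands inside the measurement interval.

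What is at stake is the pre-to-post change in fatigue for each component. Section 1.5 lists preliminary efficacy among the things to be evaluated, with seven people per component and every arm receiving an active component. If a medication change moves one participant's fatigue, for better or worse, that movement is counted in the component's pre-to-post change. In an arm of seven, a single person has visible weight.

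**Working it through.** The protocol states no figure on this point, so there is nothing to reproduce. The check sets the rules side by side and then does two short pieces of arithmetic.

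**Step 1. Who is caught by which rule?**

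| Situation at screening | Exclusion (3) / question 10 | Inclusion (8) / question 7 | Outcome |
|---|---|---|---|
| Changed disease-modifying medication last month | Caught | Not addressed | Deferred |
| Disease-modifying medication change planned for next week | Not caught (not in the past) | Not addressed (not named as part of the fatigue regimen) | Eligible |
| Changed fatigue regimen last month | Not addressed | Three-month wait after a change wanted by the person | Deferred, on a plain reading |
| Wants to change fatigue regimen during the study | Not addressed | Caught | Deferred |

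The second row is the gap. It would close without any edit only if a person's disease-modifying medication counted as part of their fatigue regimen, and the text does not say so.

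**Step 2. How long is the interval in which a change can fall?** Inputs from section 5.1: 7 days of pre-treatment surveys, about 4 weeks (28 days) of treatment, and a post assessment up to one month (taken as 30 days) after the last session.

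- Shortest: 7 + 28 + 0 = 35 days = 5 weeks.
- Longest: 7 + 28 + 30 = 65 days; 65/7 = 9.3, about 9 weeks.

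This agrees with the protocol's overall figure of about two months. Both ends are shorter than three months. A change made after the pre measure would therefore be less than three months old at the post measure, which is a recency that exclusion (3) does not allow at screening.

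**Step 3. What weight does one person carry?** Inputs from section 1.5: 7 per component, 21 in total.

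- Weight of one participant in an arm mean = 1/7 = 0.143, or 14%.
- If the medication change shifts that person's fatigue change by x, the arm's mean change shifts by x/7.

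**Step 4. How does x/7 compare with ordinary sampling noise?** The standard error of a mean of seven is SD/√7 = 0.38 SD, where SD is the between-person standard deviation of the change. Setting x/7 equal to SD/√7 gives x = √7 × SD = 2.65 SD. One affected participant would need a shift of about 2.65 SD to move the arm mean by a full standard error.

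The documents do not give x, the SD, or how often a change is already planned at screening, so the calculation stops here.

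**The case against.** The strongest reply is that a look-back stability criterion is a common and defensible choice. A participant can undertake to hold an elective fatigue treatment steady, whereas a change in disease-modifying medication may depend on the course of the disease. Exclusion (4), on recent relapse, sits beside exclusion (3) and is also look-back only. The study is described as a prospective case series, section 1.8.a names feasibility and acceptability as what it examines, and no efficacy test or threshold is stated that one participant could overturn. Assignment is random, so any such person falls into a component by chance and does not systematically favour one. All of this stands, and it keeps the priority low. It does not explain why a change known in advance should go unasked when a recent one leads to deferral.

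Several stronger readings are tempting, and the documents do not support them.

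- *A reader might infer that the protocol regards a medication change as disturbing fatigue for three months.* No reason is given for exclusion (3); it may simply mark recent disease stability.
- *A reader might infer that a change could not be dated afterwards.* The list of items on the medication form is given as examples, and the form was uploaded separately (section 5.15) and is not shown. It may already hold dates. The two forms would in any case show that a change had occurred.
- *A reader might infer that affected participants will go unhandled in the analysis.* That may be settled in a statistical analysis plan that is not at hand.
- *A reader might want a probability that at least one of the 21 changes medication.* That needs an annual rate the documents do not give. It would treat all 21 as taking such medication, which is not an entry requirement. It would also count unplanned changes, which no screening question can catch.

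**Conclusion.** The point holds in a limited form. The rule on disease-modifying medication is retrospective only, the forward-looking rule does not name it, and a person with a change already planned before the post-intervention assessment is eligible as the protocol is written. The change *can* fall in the 5 to 9 weeks between the pre and post measures; it need not.

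The effect on an arm's preliminary-efficacy estimate is x/7 per affected person. It depends on two unknowns: how far the change moves that person's fatigue, and how many people have a change planned when they are screened. The conclusion also rests on the plain reading that the fatigue treatment regimen does not include disease-modifying medication.

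Feasibility and acceptability are little affected. This is a minor, inexpensive improvement to the eligibility rules and does not threaten the study's main purpose.

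**What to change.** Reconcile exclusion (3) and screening question 10 with inclusion (8) and screening question 7, so that the protocol states whether an already planned change in disease-modifying medication counts at entry. The direct way is to add one screening question on whether such a change is planned before the post-intervention assessment, with a matching phrase in section 2.2. People who answer yes would be given the deferral the protocol already uses after a change.

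This concerns eligibility only. It asks no one to delay or alter treatment, and it does not reach changes that become necessary after enrolment.

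The cost is one phrase and one question, made by an IRB modification. The downside is that a few people are deferred.

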First, we will develop and pilot test three telehealth cognitive behavioral therapy (CBT) components for fatigue in PwMS to maximize feasibility and acceptability. We will create treatment manuals and participant materials for the following three CBT components for PwMS and fatigue:

1. *Relaxation training* (n=7): Didactic and experiential training in one or more relaxation techniques such as diaphragmatic breathing, progressive muscle relaxation, autogenic relaxation, and guided imagery
2. *Behavioral activation* (n=7): Didactic material and practice focused on identification and reduction of avoidance behaviors (e.g., excessive rest) and increased engagement in valued and reinforcing activities (e.g., physical activity, social engagement)
3. *Cognitive therapy* (n=7): Didactic material and practice focused on identifying, challenging, and modifying inaccurate and/or unhelpful patterns of thought about the self and the world (e.g., catastrophizing the meaning and consequences of fatigue) to change unwanted behavioral patterns (e.g., excessive rest)

Next, we will recruit, enroll, and randomize 21 participants. Participants will complete the baseline self-report assessment via REDCap (or by telephone, if preferred). Study staff will randomly assign them to one of three CBT intervention components noted above.

We will test each of the three components with seven fatigued PwMS (N=21) and evaluate the feasibility, acceptability, and preliminary efficacy of each component. Participants will complete the 4-session telehealth treatments by telephone or UW Zoom [Health Insurance Portability and Accountability Act (HIPAA)-compliant].

Participants will complete patient-reported outcome measures (PROMs) for pre- and post-intervention assessments via REDCap (or by telephone, if preferred). During the pre- and post-intervention assessments time periods, participants will also complete a survey consisting of four to eight questions

about their fatigue twice per day (morning and evening) for seven days via REDCap (or by telephone, if preferred). They will also complete a treatment expectancy measure after the first session via REDCap (or by telephone, if preferred). They will complete qualitative semi-structured interviews at post-intervention to contextualize quantitative data and refine the components. They will also complete a medication form by phone at the pre-treatment and post-treatment timepoints.

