- (9) Currently participating in another research study that could impact fatigue such as intervention studies targeting mood, energy management, exercise/physical activity, and diet (although participants can be screened for eligibility again once they have completed the other research study).

2.3. [DETERMINATION] Prisoners. IRB approval is required in order to include prisoners in research, even when prisoners are not an intended target population.

Is the research likely to have subjects who become prisoners while participating in the study?

For example, a longitudinal study of youth with drug problems is likely to have subjects who will be prisoners at some point during the study.

No

Yes → If a subject becomes a prisoner while participating in the study, will any study procedures and/or data collection related to the subject be continued while the subject is a prisoner?

Document Date & Version	APPLICATION IRB Protocol	Researcher Date & Version
01.26.2023 Version 4.3		05/02/2024 Version 1.5 Page 10 of 61

No

Yes → Describe the procedures and/or data collection that will continue with prisoner subjects.

Click or tap here to enter text.

2.4. [DETERMINATION] Will the proposed research recruit or obtain data from individuals that are known to be prisoners?

For records reviews: if the records do not indicate prisoner status and prisoners are not a target population, select "No". See the [GUIDANCE Prisoners](#) for the definition of "prisoner", which is not necessarily tied to the type of facility in which a person is residing.

No

Yes → Answer the following questions (2.4.a. – 2.4.d.)

2.4.a. Describe the type of prisoners, and their locations(s).

Click or tap here to enter text.

2.4.b. One concern about prisoner research is whether the effect of participation on prisoners' general living conditions, medical care, quality of food, amenities, and/or opportunity for earnings in prison will be so great that it will make it difficult for prisoners to adequately consider the research risks. How will the chances of this be reduced?

Click or tap here to enter text.

2.4.c. Describe what will be done to make sure that (a) recruitment and subject selection procedures will be fair to all eligible prisoners and (b) prison authorities or other prisoners will not be able to arbitrarily prevent or require particular prisoners from participating.

Click or tap here to enter text.

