As individual components, Relaxation Training has been shown to reduce fatigue in adults with MS, but had a smaller effect size than multicomponent CBT. Behavioral Activation is an effective treatment for depression, but telehealth behavioral activation has not been tested as a standalone intervention for fatigue in adults with MS. Likewise, Cognitive Therapy is an effective treatment for depressive and anxiety disorders, but telehealth cognitive therapy has not been tested as a standalone intervention for fatigue in adults with MS. Given that the Relaxation Training, Behavioral Activation, and Cognitive Therapy components make up telehealth multicomponent CBT for fatigue, found to be effective and acceptable, we expect that these standalone telehealth components will be acceptable and unlikely to cause emotional distress in participants.

Loss of confidentiality: There is a small risk of loss confidentiality when human subjects provide personal information. Detailed procedures to protect participant privacy are described below.

COVID-19: Of note, this study does not contribute to risk of COVID-19 infection because all study procedures, assessments and interventions are completed remotely (by telephone and/or HIPAA-compliant videoconference). There are no necessary in-person visits and/or interpersonal contact between study staff and participants.

10.2. [DETERMINATION] Reproductive risks. Are there any risks of the study procedures to subjects or partner of subjects related to pregnancy, fertility, lactation or effects on a fetus or neonate?

Examples: direct teratogenic effects; possible germline effects; effects on fertility; effects on a woman's ability to continue a pregnancy; effects on future pregnancies.

No → Go to [question 10.3.](#)

Yes → Answer the following questions:

10.2.a. Risks. Describe the magnitude, probability, duration and/or reversibility of the risks.

Click or tap here to enter text.

10.2.b. Steps to minimize risk. Describe the specific steps that will be taken to minimize the magnitude, probability or duration of these risks.

Examples: inform the subjects about the risks and how to minimize them; require a pregnancy test before and during the study; require subjects to use contraception; advise subjects about banking of sperm and ova.

If the use of contraception will be required, describe the allowable methods and the time period when contraception must be used.

Click or tap here to enter text.

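### Is it a flaw that psychotherapy for reasons other than fatigue is allowed, and that only medications are described as recorded?

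*Protocol*

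**What the plan says.** Exclusion (6) in section 2.2.b removes a person who is "Currently engaged in psychotherapy for fatigue assessed via self-report". Item 13 of the screening list in section 4.1 has the same limit: "Is the person currently engaged in psychotherapy for fatigue". Inclusion (8) in section 2.2.a asks that participants "Are willing to maintain current fatigue treatment regimen for duration of study". None of these reaches psychotherapy given for another reason.

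Exclusion (9) bars people enrolled in other research that could affect fatigue, with the examples "intervention studies targeting mood, energy management, exercise/physical activity, and diet".

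For concurrent treatment, section 5.4 describes a form used before and after treatment: "Participants will be asked questions about the medications they are taking (e.g., name, indication, dosage, dose units". The baseline and post-intervention questionnaires are given there as broad groups with examples. Section 5.15 points to uploaded documents for the forms themselves.

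Section 10.1 states that "Behavioral Activation is an effective treatment for depression" and that "Cognitive Therapy is an effective treatment for depressive and anxiety disorders". Section 1.5 says that the study will "evaluate the feasibility, acceptability, and preliminary efficacy of each component", with seven participants in each of three components (N = 21).

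**The concern.** Read together, these places suggest a gap. A participant treated for depression or anxiety in routine care could be receiving behavioral activation or cognitive therapy there, the same techniques that the study tests alone. Such a person is eligible, and no stated criterion stops that therapy from being started or changed during the roughly four-week intervention. Exclusion (9) shows that the investigators believe mood interventions can influence fatigue. If only medications are recorded, overlapping therapy would be invisible in the data.

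The preliminary-efficacy reading would be at stake. Pre-post change in a component of seven, and what participants say in interviews about perceived efficacy, might be credited to the component when part of it came from elsewhere. A treatment that was never recorded cannot be separated out later by any analysis plan.

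**Working it through.** **Do the rules conflict?** Exclusion (6) concerns treatment for fatigue in ordinary care. Exclusion (9) concerns enrolment in another study. A rule against co-enrolment can be wider than a rule about routine care without contradiction. Other parts of the protocol fit with participants having ordinary mental-health care: section 10.1 assures them that withdrawal will not harm routine care, psychotherapy included, and exclusion (5) keeps eligible people with suicidal thoughts who have neither intent nor plan.

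**Is the omission shown?** Section 5.4 lets the applicant either describe the data or upload a list of variables. The text gives category summaries and marks its examples as examples. MS disease-related variables are not itemised. The forms (section 5.15) and the manual of procedures (section 12.4) are not in the material. The visible text does not name concurrent psychotherapy, but that does not show that it is not collected. The medication form's examples include the indication, so drug treatment for mood would be visible. Only non-drug therapy is in question.

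**How large could the effect be?** Inputs: 7 per component (section 1.5), and 3 × 7 = 21 reproduces the stated total. The protocol gives no SD and no rate of outside psychotherapy, so the excess d is an assumption, in SD units of the pre-post change.

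- Weight of one participant: 1/7 = 0.143, or 14%.
- If six participants average m and one has m + d, the mean is (6m + m + d)/7 = m + d/7.
- d = 0.5: 0.5/7 = 0.07 SD. d = 1: 1/7 = 0.14 SD. d = 2: 2/7 = 0.29 SD.
- 95% CI half-width at n = 7: t(0.975, 6)/√7 = 2.447/2.646 = 0.92 SD.
- 95% CI half-width at n = 6, with that person left out: t(0.975, 5)/√6 = 2.571/2.449 = 1.05 SD.
- Shift relative to the n = 7 half-width: 0.071/0.925 = 8% up to 0.286/0.925 = 31%.

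**How often might it occur?** For an assumed share p of participants in any non-fatigue psychotherapy, the chance of at least one in a component is 1 − (1 − p)^7:

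| Assumed p | At least one of 7 |
|---|---|
| 0.05 | 30% |
| 0.10 | 52% |
| 0.20 | 79% |
| 0.30 | 92% |

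These chances include therapy that is stable throughout, which the baseline score already partly absorbs. The concern rests on therapy started or changed within the study. The protocol gives no rate for that, so the table overstates the relevant risk by an unknown amount.

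**The case for a change.** The strongest case for the concern is that recording is cheap and cannot be repaired afterwards. Staff already telephone participants before and after treatment about medications, and one question on current psychotherapy would take about a minute per call and lose no eligible person. The project exists because the active parts of CBT are unclear (section 1.8.a), so overlap with outside CBT-type therapy bears on the idea of a standalone component. In a case series each person's course is read individually, and knowing who had such therapy helps. What is collected is also a matter for the protocol, not something to leave to an analysis plan.

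Most of this stands as an argument for a useful addition. It does not show that the document is wrong. It depends on forms that are not shown and may already ask. It gives no reason why exclusion (6) must be widened. The same argument would reach routine-care changes in exercise, energy management and diet, which exclusion (9) also lists and which section 5.4 does not name either. The overlap in technique is a reason to put psychotherapy ahead of these, but only a modest one.

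**Conclusion.** The concern does not hold. Admitting people with psychotherapy for other reasons is a coherent eligibility choice. That concurrent psychotherapy goes unrecorded cannot be established from a summary that refers to separate forms.

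If it does go unrecorded, the feasibility and acceptability results, which section 1.8.a names as what this case series examines, remain sound. A preliminary-efficacy mean would move by 0.07 to 0.29 SD per affected person, against a half-width of 0.92 SD. The upper figure needs an assumed excess of 2 SD in one participant. A display with and without that participant would be descriptive only, at 7 versus 6 people, and attribution is limited anyway with seven per component and no untreated arm.

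The conclusion rests on the assumed range for d and on the concern being about therapy started or changed during the study. Asking about psychotherapy on the existing calls would be a reasonable optional addition, but the protocol has no error here to correct.
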